9.2 The PATH Intervention

Participants randomized to the PATH intervention will meet (via phone) with the interventionist around approximately day 100 post-HSCT. After the initial phone visit to introduce positive psychology and the PATH intervention, participants will be asked to complete 9 weekly positive psychology exercises. The interventionist will then meet weekly with patients via phone to review each positive psychology exercise.

PROTOCOL TITLE: Randomized Trial of a Positive Psychology Intervention for Patients with Hematologic Malignancies Undergoing Hematopoietic Stem Cell Transplantation

Table 2. PP intervention component: modules and exercises. Intervention content will be customized to HSCT context.

Module 1: Gratitude/positive affect-based exercises		
Week 1	Gratitude for positive events ⁷	Participants identify three positive events that have occurred in the past week and reflect on their feelings as they recall and describe these events.
2	Gratitude letter ⁷	Participants write a letter of gratitude thanking a person for their support or kindness.
3	Gratitude skills application	Participants select a useful activity from the prior two weeks, consider how to adapt the activity to daily life, and develop a plan to utilize this skill regularly.
Module 2: Strengths-based exercises		
Week 4	Recalling past success ⁵⁸	Participants recall an event in which they experienced success, then write about the event, their contribution to the success, and positive feelings elicited by recalling it.
5	Using personal strengths ⁷	Participants undergo a brief assessment of personal strengths, then find a specific new way to use one of their 'signature strengths' in the next 7 days.
6	Strength-based skills application	Participants select a useful activity from the prior two weeks, consider how to adapt the activity to daily life, and develop a plan to utilize this skill regularly.
Module 3: Optimism and meaning-based exercises		
Week 7	Enjoyable and meaningful activities ⁵⁹	Participants complete three activities: an enjoyable activity alone, an enjoyable activity with another person, and a meaningful activity completed alone or with others.
8	The good life ⁶⁰	Participants imagine and write in detail about a best possible (realistic) future one year from now and consider small short-term steps to take toward such a future.
9	Skills application + future planning	Participants select an activity from this module and develop a plan to utilize this skill—and additional skills from the program—this week and beyond

As shown in Table 2 above, the PATH intervention will focus on three main modules: 1) gratitude/positive affect-based exercises; 2) strengths-based exercises; and 3) optimism and meaning-based exercises.

- **Training:** The PP exercises for this trial have been identified via published literature, or directly from researchers, and modified appropriately for this population based on results from our prior work (17-154 and 18-225). Additional text outlining the rationale and instructions for each exercise are in the written packets for each exercise that are provided to participants. [name], study interventionists ([name] will be the primary study interventionist and will be covered by psychologists (Drs. [name] and [name]) who have extensive training and expertise in delivering positive psychology interventions), and CRCs will engage in several training exercises prior to study initiation. [name] and [name] (research mentor) have had substantial experience in delivering PP exercises from prior work which will inform training of other study team members. Together with [name], [name] will also review the treatment manual and the team's prior training manuals related to these exercises.
- **Ensuring Fidelity of the PATH Intervention:** We will take several measures to ensure the fidelity of our study design and intervention delivery. (Table 3) For the study design, we will use a well-established intervention guide utilized in prior studies by our group and pilot-tested in this population (18-225), and monitor the number of participants in our control group. Also, we will use rigorous training procedures for our CRCs. To ensure fidelity of the intervention delivery, the PI will meet weekly with [name], her primary research mentor for the study and a world leader in PPI development for patients with serious illnesses. [name] will provide ongoing training on effective and consistent delivery of positive psychological exercises to participants and will help to problem-solve issues as they come up during the intervention delivery. We will audio-record all sessions and use a fidelity structure developed from prior work^{17, 54} to measure the extent to which domains of each session are addressed. On a monthly basis, Drs. [name] and [name] (research mentor) will independently review (and rate for

PROTOCOL TITLE: Randomized Trial of a Positive Psychology Intervention for Patients with Hematologic Malignancies Undergoing Hematopoietic Stem Cell Transplantation

fidelity, using an adapted scale) a random sample of 10% of the audio-recorded sessions to ensure intervention fidelity.

Table 3: Fidelity	Steps Taken to Ensure Fidelity	Fidelity Assessment
Study Design	
 - Intervention based on extensive literature review, prior work in several medical populations and pilot trial in this study population - Standard intervention dose with clear feasibility data based on prior work 	
 - Utilize evidence-based positive psychology intervention guide based on prior trials - Measure number of intervention visits
Intervention Delivery	
 - Utilization of prior tested positive psychology intervention guide with standardized content areas - Audio-record all intervention calls and sessions 	
 - Study PI and interventionist will meet with primary mentor for this project and positive psychology intervention expert [name] weekly for ongoing training of consistent intervention delivery - [name] will help problem-solve issues as they come up during the intervention delivery - On a monthly basis, Drs. [name] and [name] will independently review (and rate for fidelity, using an adapted scale) a random sample of 10% of the audio-recorded sessions to ensure intervention fidelity

9.3 Usual Care Control

Positive psychological interventions are not part of the routine psychosocial support for patients undergoing HSCT. Hence, due to the focus of feasibility for this trial, we will use a usual care control condition which entails regular social work assessments as part of the HSCT recovery. Routinely, allogeneic transplant recipients are evaluated by a social worker prior to their transplant and the social worker is available to meet regularly during their recovery; typically, social workers see patients once every 2-3 months, and their work does not focus on PPWB skill building or cognitive strategies. Participants in both conditions can see the social worker and receive any other treatments for mental or physical health, as desired. We will track social work visits and other supportive care measures (including any visits with mental health clinicians) in both groups. Data collected on social work consultations will be considered as covariates in our analyses.

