1.2 Specific Aims/Objectives

#1 (Feasibility; Primary Aim): To determine the feasibility and acceptability of the PATH intervention in patients with hematologic malignancy undergoing HSCT.

PROTOCOL TITLE: Randomized Trial of a Positive Psychology Intervention for Patients with Hematologic Malignancies Undergoing Hematopoietic Stem Cell Transplantation

Hypothesis: The PATH intervention will be deemed feasible with >75% of participants randomized to the intervention arm completing ≥ 6/9 positive psychology exercises. The PATH intervention will be deemed acceptable with mean ease and utility scores of each exercise being ≥ 7/10.

#2 (Effects on Patient-Reported Outcomes): To assess the preliminary efficacy of the PATH intervention on psychological (e.g., depression, anxiety, optimism, positive affect), QOL, and functional outcomes compared to the usual care condition.

Hypothesis: Patients randomized to the PATH intervention will have improved PPWB (e.g., optimism, positive affect, gratitude), mood (e.g., depression and anxiety), and QOL compared to those in the usual care condition.

#3 (Effects on Health Behaviors): To examine the impact of the PATH intervention on behavioral outcomes (e.g., medication adherence, physical activity) compared to those in the usual care condition.

Hypothesis: Patients randomized to the PATH intervention will have improved behavioral outcomes (e.g., medication adherence, physical activity) compared to those in the usual care condition.

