Participants will be registered with the Clinical Trials Management System after they have consented, provided baseline *Actigraph GT3X+* data, and completed baseline assessments. If participants provide consent but do not complete baseline Actigraph data collection and assessments, they will not count towards accrual numbers. Participants who withdraw from the study or die during the study period will not be replaced and they will count towards accrual numbers.

DF/HCC institutions will register eligible participants in the Clinical Trials Management System (CTMS) Oncore as required by DF/HCC SOP REGIST-101. Registration must occur after the initiation of protocol-specific procedures or assessments.

For registration of participants from the DF/HCC institutions, study staff will complete the DF/HCC protocol-specific eligibility checklist. Study staff will confirm that the participant meets all inclusion criteria as described in this protocol. Study staff will then register study participants through OnCore. Study staff will follow DF/HCC Standard Operating Procedure for Human Subject Research Titled *Subject Protocol Registration* (SOP #: REGIST-101) and register the participant on the protocol.

Once the patient has been registered, a member from the MGH Cardiac Psychiatry Research Program (CPRP) team or the Cancer Outcomes Research and Education Program (CoRE) (independent from the study staff) will perform randomization procedures using a computer-generated randomization schema, stratified by GVHD status.

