We will compare between-group differences in change over time in all patient-reported outcome measures (i.e., psychological, functional, and QOL outcomes) at the 9 and 18-week time points using random effects regression models with a random intercept for each patient. Longitudinal analyses will include all time points. The model will include a categorical effect of time (baseline, week 9 and week 18), a group effect and a time by group interaction. The time by group interaction will estimate the difference in the change from baseline to each time point, and these regression coefficients will be the focus of the analysis.

Given that this pilot is not powered to detect statistically significant group differences, we will examine difference in the change with time and sample variance components on the secondary outcomes. Effect sizes (Cohen's d) will be calculated for changes in outcomes from baseline to 9 and 18 weeks, where 0.3 indicates a small effect, 0.5 a medium effect, and 0.8 a large effect.⁸⁸ Effect sizes will be used in a power analysis to estimate the necessary sample size to conduct a full-scale efficacy trial with power >80%. We will also verify the needed sample size based on ability to detect a clinically meaningful difference and references to existing literature.⁸⁹

Finally, we will explore (1) possible mediators of the intervention (e.g., coping strategies) by examining the bootstrapped confidence intervals of the indirect effects and (2) possible moderators (e.g., social support) of intervention effects by probing interactions between the moderator and group assignment that reach or approach significance ($p<0.15$) when predicting patient-reported outcomes.

PROTOCOL TITLE: Randomized Trial of a Positive Psychology Intervention for Patients with Hematologic Malignancies Undergoing Hematopoietic Stem Cell Transplantation

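### Section 9.3 would consider social-work use during the trial as a covariate: PATH may affect it, the Section 10.1 model omits it, and adjusting for it can bias the between-group effects

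*Combined protocol and SAP*

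**What the plan says.** Section 9.3 describes the comparator as "a usual care control condition which entails regular social work assessments as part of the HSCT recovery" and adds that "typically, social workers see patients once every 2-3 months". Access is open in both arms: "Participants in both conditions can see the social worker and receive any other treatments for mental or physical health, as desired". Use is then recorded: "We will track social work visits and other supportive care measures (including any visits with mental health clinicians) in both groups". The next sentence gives the analytic intention: "Data collected on social work consultations will be considered as covariates in our analyses". It names no analysis, functional form or time restriction.

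Section 10.1 (Specific Aim 2) specifies the efficacy model for patient-reported outcomes as a random-intercept regression: "The model will include a categorical effect of time (baseline, week 9 and week 18), a group effect and a time by group interaction". The interaction coefficients are the quantities of interest, and no covariate is listed. Under Missing Data, the same section commits to intention to treat with all randomised participants. It also says that Cohen's d values for change will feed the sample size of a full-scale trial.

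**The concern.** Visits tracked by study group are, at least in part, post-randomisation data. Allocation follows registration (Section 5.1: "Once the patient has been registered, a member from the MGH Cardiac Psychiatry Research Program (CPRP) team"), and the tracking then runs while PATH is being delivered.

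The protocol gives reasons why PATH might change use in either direction:

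- Aim 2 in Section 1.2 hypothesises that "Patients randomized to the PATH intervention will have improved PPWB (e.g., optimism, positive affect, gratitude), mood (e.g., depression and anxiety), and QOL". Better mood could reduce demand for social work.
- Only the PATH arm has nine weekly calls, and Section 13.0 has staff escalate persistent distress to the investigator and the transplant clinician. Closer contact could therefore raise use.

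Because patients may seek visits as they wish, use may also follow distress, which is itself an outcome (HADS). A contrast adjusted for such a variable is not the total effect of assignment, and randomisation does not protect it.

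Sections 9.3 and 10.1 also point to different models. An analyst could follow either one and could choose after seeing the results. At stake are the secondary between-group estimates and the effect sizes carried into the next trial.

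**Working it through.** **The plan's own figure.** Section 10.2 gives d = 0.74 as detectable with 80% power and 30 completers per arm. A two-sample t-test at two-sided 0.05 gives d = 0.736, and power at 0.74 is 80.5%. The figure reproduces. The point does not depend on it, and dropping the covariate does not change it.

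**Inputs.** From the documents: the Section 10.1 model, three time points, and one visit per 2-3 months. Eighteen weeks is about 4.1 months, so about 4.1/3 = 1.4 to 4.1/2 = 2.1 visits are expected. The documents do not say how far PATH shifts use or how use relates to outcome. Everything below on those two points is assumed.

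**Algebra at a single time point.** Let A be arm, U unmeasured distress after baseline, S post-randomisation use (within-arm SD 1), and Y the outcome, with higher values better:

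- S = aA + bU + error
- Y = tA + gS + uU + error
- total effect = t + ga
- effect adjusted for S = total - a(g + ub)

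With an assumed total effect of 0.50:

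| Assumed mechanism | g + ub | a = -0.3 | a = -0.5 |
|---|---|---|---|
| Distress drives use and outcome (b = 0.5, u = -0.5, g = 0) | -0.25 | 0.50 - 0.075 = 0.425 | 0.50 - 0.125 = 0.375 |
| Visits help the outcome (g = 0.3, b = u = 0) | 0.30 | 0.50 + 0.09 = 0.59 | 0.50 + 0.15 = 0.65 |
| Both (g = 0.3, b = 0.5, u = -0.5) | 0.05 | 0.515 | 0.525 |

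With a = 0 every entry is 0.50. If PATH raises use (a = +0.3), the signs reverse: 0.575, 0.41 and 0.485.

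**The Section 10.1 model.** The focus there is the time-by-group interaction, so the form in which use enters matters. Week 9 / week 18 interaction terms from simulated trials (6,000 patients, complete data, true total effect 0.50, a = -0.5; small departures from 0.50 are simulation error):

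| How use enters | Distress mechanism | Helpful-visit mechanism |
|---|---|---|
| Not at all | 0.522 / 0.502 | 0.486 / 0.492 |
| Average use, main effect only | 0.522 / 0.502 | 0.486 / 0.492 |
| Time-varying use | 0.431 / 0.415 | 0.649 / 0.638 |
| Average use by time | 0.311 / 0.298 | 0.644 / 0.645 |

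A time-invariant main effect acts between patients, while the interaction is estimated from within-patient change, so it leaves the interaction alone. With 15% random dropout added, the two versions still agreed to within 0.001.

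The 0.311/0.298 entry falls below 0.375 because averaging two periods shrinks the within-arm variance of use to 0.25 + 0.75/2 = 0.625. The slope becomes -0.25/0.625 = -0.4, and the adjusted effect is 0.50 - (-0.5)(-0.4) = 0.30. With a = 0 and the distress mechanism, no form moved the terms by more than 0.001.

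**What this means for planning.** By n per arm = 2(1.96 + 0.84)²/d², about 15.7/d² (80% power, two-sided 0.05), d = 0.50 needs 63 per arm, d = 0.375 needs 112 and d = 0.65 needs 38.

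**The case against.** The best defence is that no adjustment is promised. Section 9.3 speaks of considering a covariate, while Section 10.1 states the model without one, makes its interaction terms the focus and adds intention to treat. Read together, the main estimate is unadjusted. That is a fair reading. It leaves an unspecified analysis to be reconciled, not a committed error.

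Several stronger readings are tempting, and the documents do not support them:

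- *That PATH's effect would be understated.* This assumes one mechanism. If visits help, or if PATH raises visits under the distress mechanism, the bias reverses. With both paths it nearly cancels, and without a shift in use it is zero.
- *That any adjustment biases the planned estimate.* The simplest form, total use as a main effect, does not move the time-by-group terms materially.
- *That adjusting removes the comparator.* Social work is background care open to both arms, so the contrast is PATH added to it.
- *That visits are driven by distress.* Section 9.3 describes largely routine assessments at long intervals, with room for patient-initiated use. Routine scheduling weakens both links that the bias needs.
- *That the trial's main conclusion is at risk.* Feasibility and acceptability are judged in the PATH arm alone. Section 10.1 calls the trial unpowered for group differences, does not say the effect sizes would be covariate-adjusted, and also checks the next sample size against a clinically meaningful difference.

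What stands is that nothing in Section 9.3 excludes post-randomisation visits or the forms of adjustment that do cause bias.

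**Conclusion.** The point holds as an unresolved inconsistency that opens a route to bias, not as a demonstrated bias. Adjusting for post-randomisation social-work use would depart from the intention-to-treat effect whenever PATH changes use and use is related to outcome.

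Size and direction cannot be fixed from the documents. Under the assumptions shown, a true d of 0.50 would be reported as 0.375 to 0.65 in a single-time-point adjusted comparison. In the random-intercept model the illustrative range runs from about 0.30 (average use interacting with time) to about 0.65, and a main effect alone gives essentially no change. Zero bias belongs in the range.

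Only the secondary between-group comparisons and the effect sizes used for planning are exposed. This is a modest, easily corrected weakness in the specification of the analysis.

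**What to change.** Replace the covariate sentence in Section 9.3 with:

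> Social-work and mental-health contacts after randomisation will be summarised by arm as concomitant care and will not be covariates in the main efficacy models; only contacts before randomisation may be used as a baseline covariate. Any analysis using post-randomisation contacts will be labelled exploratory (mediation or sensitivity).

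Keep the Section 10.1 model as the main estimate of the group difference. It need not be the only one: the completer analysis and the missing-data sensitivity analyses already planned there can stay, and the exploratory mediation work is a natural place for post-randomisation contacts. If a pre-randomisation contact count is to be used, Section 10.1 should name it so that the two sections agree.

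The cost is one sentence and one descriptive table. The visits are already to be tracked, and neither the sample size nor the detectable d = 0.74 changes.

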9.4 Selection of Instruments

We have selected self-assessment measures based on our prior work and the conceptual framework of our intervention which seeks to improve psychological outcomes, QOL, fatigue, coping strategies, and health behaviors in patients recovering from an allogeneic stem cell transplant.

1.1.1. **Demographics:** Patients will complete a demographic questionnaire at baseline detailing their age, sex, race, ethnicity, religion, relationship status, educational level, annual household income, and living situation. (Appendix G)

1.1.2. **QOL:** We will use the 47-item Functional Assessment of Cancer Therapy-Bone Marrow Transplant (FACT-BMT) to assess QOL, which has been validated for use in patients undergoing HCT.⁶¹ The FACT-BMT consists of five subscales assessing well-being across four domains (physical, functional, emotional, social, and bone marrow

PROTOCOL TITLE: Randomized Trial of a Positive Psychology Intervention for Patients with Hematologic Malignancies Undergoing Hematopoietic Stem Cell Transplantation

transplant symptoms). These self-reported measures possess strong psychometric properties and have been validated for patients undergoing HSCT. (Appendix H)

- 1.1.3. **Fatigue:** We will use the Patient Reported Outcome Measurement Information System-Fatigue-8a (PROMIS-Fatigue-8a) questionnaire to assess fatigue. The PROMIS-Fatigue-8a is a 7-item well-validated fatigue scale for patients undergoing HSCT. Higher scores indicate greater fatigue.⁶² (Appendix I)
- 1.1.4. **Overall Function:** We will use the 20-item Patient-Reported Outcomes Measurement Information System-Physical Function-20 (PROMIS-PF-20); higher scores indicate better physical function.⁶³ (Appendix J)
- 1.1.5. **Mood:** We will use the Hospital Anxiety and Depression Scale (HADS) to assess symptoms of depression and anxiety in all study participants. The HADS is a 14-item questionnaire that contains two 7-item subscales assessing depression and anxiety symptoms during the past week (Appendix K).⁶⁴ Used extensively in samples of patients with cancer, the questionnaire consists of a four-point item response form that quantifies the degree to which participants experience mood symptoms. Scores on each subscale range from 0 to 21, with a cutoff of 8 or greater denoting clinically significant anxiety or depression.
- 1.1.6. **PTSD symptoms:** We will use the Post-Traumatic Stress Disorder Checklist (PCL) to assess symptoms of post-traumatic stress in patients. The PCL is a 17 item self-reported measure that evaluates symptoms of post-traumatic stress disorder according to the criteria of the Diagnostic and Statistical Manual of Mental Disorders-IV.⁶⁵ (Appendix L)
- 1.1.7. **Optimism:** We will use the 10-item Life Orientation Test-Revised (LOT-R) to measure dispositional (trait) optimism. Higher scores indicate greater optimism.⁶⁶ (Appendix M)
- 1.1.8. **Positive Affect:** We will use the 10-item Positive and Negative Affect Schedule (PANAS) to measure positive affect; higher scores indicate greater positive and negative affect.⁶⁷ (Appendix N)
- 1.1.9. **Social Support:** We will assess social support using the 26-item Social Support Effectiveness Questionnaire (SSEQ), a validated instrument used in oncological population to assess patients' perception of social support.^{68, 69} (Appendix O)
- 1.1.10. **Coping strategies:** We will use the Brief Cope, a 28-item questionnaire that assess 14 methods of coping (e.g., self-distraction, humor, denial) using a 4-point Likert scale.⁷⁰ (Appendix P)
- 1.1.11. **Satisfaction:** We will use the 5-item Satisfaction with Life Scale (SWLS) to measure satisfaction with life; higher scores indicate greater satisfaction with life.⁷¹ [Appendix Q]

PROTOCOL TITLE: Randomized Trial of a Positive Psychology Intervention for Patients with Hematologic Malignancies Undergoing Hematopoietic Stem Cell Transplantation

1.1.12. **Gratitude:** We will use the 6-item Gratitude Questionnaire to measure dispositional gratitude; higher scores indicate greater proneness to experience gratitude in daily life.⁷² [Appendix R]

1.1.13. **Purpose and Flourishing:** We will use the 8-item Flourishing Scale to assesses a person's self-perceived success in critical areas such as engagement, relationships, self-esteem, meaning & purpose, and optimism; higher scores indicate many psychological resources and strengths.⁷³ [Appendix S]

1.1.14. **Health Behaviors:** Physical activity and medication adherence will be the target behavioral outcome measures. We will use the well-validated Actigraph GT3X+ accelerometer,⁷⁴ at baseline, Week 9, and Week 18, for 7 days of wear; minimum acceptable use is 4+ days with 10+ hours of recorded data as in prior guidelines⁷⁵⁻⁷⁷ to measure minutes/day of light activity (100-1951 counts/min⁷⁸) as our primary activity measure, along with sedentary leisure time (SLT),^{74, 79} given their links to health outcomes. Medication (specifically immunosuppressant, tacrolimus or sirolimus) adherence will be measured via the widely used electronic pill monitoring system, MEMS Caps,⁸⁰ to electronically monitor immunosuppressant adherence over the duration of the study. From the EHR and confirmed by patients, we will determine immunosuppressant medication and dosing, and we will calculate changes in adherence over time (% of medication correctly taken, by week and month), based on MEMS data. Additionally, we will assess self-reported adherence to Tacrolimus (an immunosuppressant medication which all allogeneic HSCT patients must take) with the Medication Adherence Scale-5 (MARS-5).^{81, 82} (Appendix T)

9.5 Data from the Electronic Health Record:

Study staff will collect clinical, disease, and transplant characteristics at baseline including: ECOG Performance Status at the time of HSCT, clinical comorbidities as measured by the HCT-Comorbidity Index,⁸³ underlying diagnosis, date of diagnosis, disease status at the time of HSCT, disease risk based on the Disease Risk Index,⁸⁴ conditioning regimen, donor type, donor source, date of HSCT, and hospital length-of-stay. We will also collect data on the incidence and severity of acute and chronic GVHD and the incidence of relapse at one year post-HSCT as these outcomes are associated with QOL.

